COVER PAGE

CDX 19-001

PI: [name], MD

Improving Outcomes for Older Veterans with Chronic Back Pain and Depression- Aim 3

Protocol, last approved 3/9/2021

The Investigator's Protocol, IRB 18-041

1. Title

Improving Outcomes for Older Veterans with Chronic Back Pain and Depression- Aim 3

2. Principal Investigator and Co-Investigators

[name]- Principal Investigator

3. Sponsor of the Study

VACO: VA HSR&D

4. Investigational New Drug (IND) / Investigational Device Exemption (IDE)

Not Applicable

5. Purpose of the Study, Including the Hypothesis to be Tested

The overarching goal of this study is to develop and evaluate a telephone delivered behavioral change intervention for older Veterans with chronic low back pain (cLBP) and comorbid depression, and to ultimately assess its effect on cLBP-related pain, depressive symptoms, and disability. An additional component of this study will include a texting-based intervention to assess the feasibility of a texting program in monitoring Veterans with cLBP and comorbid depression.

Aim 3: Conduct a pilot RCT to assess feasibility for older Veterans with cLBP and depression assigned to receive the behavioral interventions (n=25) versus waitlist control (n=25). For participants assigned to the intervention arm, trained health coaches will deliver the intervention via telephone. All participants, regardless of what group they have been assigned to will undergo several outcome assessments (pre-screening, baseline, mid-point, final assessments) conducted by a blinded research assistant. Subjects randomized to the waitlist control group will be offered the same intervention once the active intervention group has completed the active sessions and assessments.

Annie pilot: Assess the feasibility of a texting-based protocol to assess outcomes (steps, pain, mood) among older Veterans with cLBP and depression among a subset of the larger pilot RCT (n=10-15). This will occur in two phases. The first phase (development) will involve asking up to five veterans who have completed MOTIVATE to give us feedback on usability and understandability of the proposed texting system. The second phase involves answering the texting questions to evaluate feasibility of the texting program (in a sample of 7-10 Veterans); this will be followed by in-depth semi-structured interviews to gather more information about barriers and facilitators of using the texting program.

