Timing of assessments/ data collection: The research staff will screen, identify eligible Veterans for the study, obtain consent (either in person or verbally (over the phone) initially followed by mailed written consent), and complete further screening for eligibility. If the subject is eligible for this study, the research staff will arrange a separate phone call for a baseline assessment via telephone. The baseline interview must be completed within 2 weeks for the participants to proceed to the intervention. This time frame may be extended at the discretion of the study team. Once the baseline visit is complete then the patient will be informed if randomization allocation.

As seen in the Figure below, the health coaches will conduct the once a week session (or every two weeks depending on the session content) sessions (11 in total), delivered via telephone. A research team member, not the individual conducting the intervention sessions, will complete all assessments via telephone using a structured data collections tool at baseline, 5 weeks (mid-point assessment), at 10 weeks (post intervention

session), 6 months and 12 months post-intervention. Those in the Annie texting-pilot will participate for the duration that the MOTIVATE sessions are typically provide to the waitlist control group (8 sessions over 12-20 weeks). The study team will also conduct interviews as outlined above at 6 months and 12 months to obtain feedback regarding implementation and sustainability of the behaviors learned. The data from these assessments will be entered into a VA Redcap database <https://vhacdwweb05.vha.med.va.gov/> that is housed behind the VA firewall on secure research folder on VA servers:

<\\v17.med.va.gov\\v17NTX\\Services\\Research\\[name]-Research>. All data entered into Redcap is de-identified. Following the physical activity session, the health coach or research staff will obtain daily versus weekly step counts that the subject will read out over the phone. Total steps taken will be documented within 1 week, and then at during subsequent health coaching sessions as well as the 10 week assessment by research staff.

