- Comorbidities will be obtained from CPRS, prior to baseline, using the previously validated self-report version of the Charlson index;
- Substance use will evaluate for alcohol abuse (Short Michigan Alcoholism Screening Test), and illicit substance use (Drug Use Questionnaire [DAST-10] that was found previously to negatively impact outcomes;
- Mild cognitive impairment (MCI) - subjects not excluded based on the telephone Memory Impairment Screen will be screened for the presence of MCI with a Six-Item Screener. Prior research demonstrates that cognitive function mediates the relationship between pain and physical performance in older adults with cLBP. This may also impact adherence to behavioral interventions;
- Future Time Perspective scale consists of 10 statements about the subjective perceptions of time and is most commonly used to assess time horizons;
- Medications (see below for more details);
- Body mass index will be obtained from CPRS; Self-report of pain, physical/psychological/social function, quality of life (see primary/secondary outcomes).
- Sleep: PROMIS SF 6-item questionnaire to assess sleep
- Resilience: Connor Davidson Resilience Short Form: CDRISC 10 item that assesses resilience
- Patient Satisfaction Survey – six questions about the subject's experience in the study that will be asked at the end assessment
- Texting response rates of Veterans via Annie dashboard.
- Trends of step counts, pain scores, and mood scores overtime via the Annie texting dashboard
- Patient satisfaction survey among Annie texting pilot - questions on the about the subject's experience will be asked at the end of the assessment

Primary Feasibility Outcome Measures in Aim 3: Feasibility outcomes will be useful for the planning a hybrid effectiveness/implementation merit IIR award. These outcomes include: enrollment rates across different primary care clinics at Dallas VAMC; intervention adherence (measured as number of sessions the subject engaged in) and retention; use trends of Annie texting over time.

Upon completion of the intervention, a member of the research team (not the individual conducting the intervention sessions) will conduct in-depth semi-structured interviews and will also seek ratings of the helpfulness of skills taught (Likert scale), overall satisfaction, and whether the information presented provided appropriate motivation to continue practicing learned skills. The data collected from these

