- Global impression of change will be assessed using the Patient Global Impression of Change Scale, a 7-point scale (1 = No change (or condition has gotten worse) to 7 = great deal better and a considerable improvement that has made all the difference) asking participants to rate their change (if any) in pain since starting the study.
- Pain Stages of Change Questionnaire (PSOCQ) evaluates attitudes, intentions, and behaviors consistent with stages of change for pain self-management.
- Therapeutic alliance will be assessed using the Working Alliance Inventory Short-Form will measure therapeutic relationship between patients and therapist (health coach in our study). To allow the therapeutic relationship to develop, subjects will complete this assessment starting at 5 weeks.
- Sleep: PROMIS SF 6-item questionnaire to assess sleep
- Resilience: Connor Davidson Resilience Short Form: CDRISC 10 item that assesses resilience
- Annie texting system: A select group of subjects will receive text messages to collect their step counts, pain scores, and mood levels

Analyses for Aim 3: Feasibility outcomes will be measured by recruitment rates, adherence, retention and intervention fidelity. For Aim 3 we will add prompts during the semi-structured interviews that focus on

how subjects, if applicable, achieved an increase in physical activity. For example, did they build more walking- based activities in their daily routine (walking to the store rather than driving) or did they add new activities to accumulate more steps? We will also inquire about whether goals achieved were congruent with motivations to change behavior and how these motivations may influence sustained behavior. Fidelity assessment, as described above, will result in feedback to the health coaches and will ensure that the health coaches deliver the intervention as intended.

For the Annie pilot, feasibility will be tested in phase I and phase II. In phase I, a small group of Veterans and experts will be asked open-ended questions on their thoughts of the Annie system. The Annie texting protocol will be modified so it best serves the needs of veterans. In phase II, feasibility will be assessed by looking at response rates through the Annie dashboard. At the end of phase II, structured interviews will take place among the participants regarding their opinions, barriers, and thoughts for improvement of the Annie texting system as tool to assist in pain management.

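### The plan calls outcome assessment blinded, but from week 5 the telephone battery includes a health-coach alliance scale that reveals the arm, possibly before the 10-week RMDQ and PHQ-9 are taken

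*Combined protocol and SAP*

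**What the plan says.** Section 5 describes "several outcome assessments (pre-screening, baseline, mid-point, final assessments) conducted by a blinded research assistant", for participants in both groups. The words at issue are "conducted by a blinded research assistant".

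Section 12, under the timing of assessments, describes the caller differently: "A research team member, not the individual conducting the intervention sessions, will complete all assessments via telephone". The follow-up times begin with "5 weeks (mid-point assessment), at 10 weeks (post intervention" session, then 6 and 12 months. The word blinded does not appear there. The only stated requirement is that the caller is not the coach.

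Section 13 lists the instruments. Among them is the Working Alliance Inventory, which measures the "therapeutic relationship between patients and therapist (health coach in our study". To let that relationship form first, "subjects will complete this assessment starting at 5 weeks". Section 13 also lists a six-question satisfaction survey about the participant's "experience in the study that will be asked at the end assessment". Section 12 has step totals recorded at coaching sessions "as well as the 10 week assessment by research staff".

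Section 12 also states that the waitlist group stays on usual care without the active intervention. Participants learn their allocation after the baseline visit, but the section does not say who tells them.

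**The concern.** An assessor is blinded only if nothing in the assessment discloses the arm. A scale about the participant's relationship with a health coach has no meaning for someone without a coach. Putting it in the assessor's own battery works against the statement in Section 5.

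RMDQ and PHQ-9 are collected by voice over the telephone, so a caller who knows the arm can influence answers through tone, prompting or handling of hesitant replies. Section 13 uses the between-arm difference in change on these two scales to estimate a preliminary effect size and its variance, and names both as primary outcomes for a future effectiveness trial. If the pilot is reported as having blinded assessment when its procedures do not secure it, those planning the next trial will give the estimate more credit than it has earned.

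**Working it through.** The documents give no figure to reproduce, and no arithmetic applies. The check sets out who calls, what is asked and when.

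1. **Who calls.** Section 5 uses the singular, a blinded research assistant. Section 12 twice uses the singular, a research member or team member other than the coach, who calls all participants whatever their group and completes all assessments. No text gives any instrument to a second person.
2. **Week 5.** Of the items that might reveal the arm, only the coach-alliance scale is documented at this call.
3. **Week 10.** The alliance scale is due again, and research staff record step counts. The satisfaction survey comes at the end assessment.
4. **Does the alliance scale reveal the arm?** If it is put to everyone, controls must say that they have no coach. If it is put only to coached participants, its presence or absence on the form shows the arm. Each route discloses it.
5. **Do step counts reveal the arm?** Section 11 has the pedometer mailed between coaching sessions 1 and 2, which points to the intervention arm only. Section 13 describes pedometer wear for participants generally and says it is explained at recruitment. The text does not settle this, so step counts may add to the problem.
6. **Consequence for the 10-week RMDQ and PHQ-9.** This depends on two things that the documents leave open: whether one person makes both calls, and the order of instruments within a call.

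| Caller at weeks 5 and 10 | RMDQ and PHQ-9 before alliance scale at week 10 | Alliance scale before RMDQ and PHQ-9 at week 10 |
|---|---|---|
| Same person | Arm known since week 5 | Arm known |
| Different people who do not share the information | Arm not revealed by this item | Arm known |

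Three of the four arrangements leave the caller unblinded for the 10-week outcomes. This counts possibilities and is not a probability. The singular wording in Sections 5 and 12 favours the first row, where instrument order at week 10 makes no difference.

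7. **Which analysis is exposed.** Section 13 compares change from baseline to 3 months, while the schedule has a 10-week assessment and no 3-month one. Either time falls after week 5, so the mismatch does not affect this point.
8. **Safeguards looked for.** The documents state no instrument order, no separate staff member for arm-specific items, no instruction to participants about disclosing their arm, and no check of whether blinding held.

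**The case against.** Four arguments on the other side deserve weight.

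- **The call script is not among the documents.** Section 12 refers to a structured data collection tool, which may already put RMDQ and PHQ-9 first, and different people may make the two calls. This stands as a limit: unblinding before the 10-week outcomes is conditional. It does not remove the conflict, because the plan claims blinding without stating the conditions that it needs.
- **Participants know their arm.** RMDQ and PHQ-9 are self-reports, so blinding the caller removes only part of the possible bias. This stands.
- **The comparison is exploratory.** The primary outcomes are feasibility measures such as enrollment, adherence and retention, and caller blinding does not bear on them. This stands, and it limits the importance of the point.
- **The other items are weaker evidence.** Step counts may be collected in both arms. The satisfaction survey asks about being in the study, which waitlist participants also are, so it is not shown to be arm-specific.

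A reader might infer more than this: that alliance, satisfaction and step items are all asked at both calls, or that every later RMDQ and PHQ-9, including those at 6 and 12 months, is unblinded. The documents do not support either. Only the alliance scale is documented at week 5. Section 5 does not name the 6- and 12-month contacts in its blinding statement, and by then waitlist participants may have been offered the intervention. It is also tempting to express the bias as a fraction of the confidence interval, but the documents give no basis for any assumed shift.

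**Conclusion.** The concern holds in a limited form. Section 5 claims blinded assessment at the mid-point and final calls, while the battery in Sections 12 and 13 contains a coach-alliance scale from week 5 that discloses the arm. For the 10-week RMDQ and PHQ-9, the claim fails if the same person makes both calls, which the wording suggests, or if the scale precedes those outcomes at week 10. Step counts add to this only if pedometers are limited to the intervention arm.

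The conclusion assumes that the alliance scale is part of the calls made by the outcome assessor, as the statement that one team member completes all assessments implies. The direction and size of any bias are unknown. What is affected is the set of exploratory between-arm effect sizes for RMDQ and PHQ-9, and the accuracy of describing them as blinded. The primary feasibility outcomes are not affected. The change is worth making because it is cheap and the estimates are meant to inform a later trial.

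**What to change.** 1. In every call, ask RMDQ, PHQ-9 and the other self-report outcomes first, and lock those REDCap forms before any arm-specific item appears.
2. Have an existing team member who does not collect those outcomes administer the alliance scale. Reordering alone is not enough, because what a caller learns at week 5 carries over to week 10.
3. State whether the waitlist arm has pedometers during the comparison period. If not, give the week-10 step count to the same second person.
4. Name that person, not the assessor, as the one who tells participants their allocation.
5. If staffing does not allow this separation, replace the description in Section 5 with *assessor independent of intervention delivery* and report the follow-up RMDQ and PHQ-9 as not blinded.

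Items 1 to 4 cost a rearranged form and a short extra contact or hand-over by existing staff. The documents do not show how many team members are available, which is why item 5 is offered. Its cost is a less favourable description of the assessment. Neither route changes the sample size or the analysis.

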In this study, the sample will be identified and enrolled using a multi-step screening process, very similar to successful recruitment processes that [name] mentoring team has used within the VA system. The population of interest for this study is older Veterans (65 years of age and older) with comorbid chronic back pain and depression. Please see Section 6 above for background and justification for why we chose to focus on these chronic conditions in older Veterans. Both are exceedingly prevalent conditions that lead to considerable morbidity in this aging population. Please see Section 8 below for more detail on how cLBP will be defined and subjects selected.

8. Subject Selection, Inclusion and Exclusion Criteria

The eligibility criteria for all Veteran participants are as follows: Veterans who are 65 years or older, with an ICD-10 code for back pain (cLBP) on the problem list who are patients of primary care clinics at the Dallas VA (including community based outpatient clinics). A list of potentially eligible participants will be obtained from the VA corporate data warehouse to verify the presence of a diagnosis of cLBP (by ICD-10 code initially) in the prior 2 years with at least 1 visit for cLBP in the last year.

There will be three potential **recruitment strategies (described in detail in section 12)**, based on what we learned was most effective during Aim 1 and Aim 2 of this study. The *first* method involves: all veterans who meet

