- Depression, PHQ-9 \geq 10 stable (per chart review, no psychotic or suicidal ideation; confirmed over telephone)
- Capable of participating in home-based activity
- Has a smart phone with texting ability to participate in the Annie texting pilot

Exclusion Criteria:

- No telephone
- Not English speaking
- Unwilling to be randomized to either study arm
- Self-reported uncorrected hearing or visual disturbance precluding ability to participate in telephone sessions or read pedometer screen
- Cognitive impairment assessed by Memory Impairment Screen
- Lumbar surgery within the last year

- Self-reported dependence on wheelchair, bed-bound, or severe balance impairment (unable to participate in physical activity intervention)
- Illness requiring hospitalization within the last 3 months that interferes with a home based physical activity intervention. Specific question: Have you been hospitalized for an illness in the past 3 months that would make participating in a physical activity program challenging or unsafe? (Examples include: fall, gout attacks, stroke, heart attack, heart failure, or surgery for blocked arteries)
- Suicidal ideation, prior psychotic episodes requiring hospitalization within the last year

Veterans receiving mental health services at the time of the study recruitment will not be excluded. All mental health treatments and health service-use characteristics will be included in the study analyses as covariates.

9. Number of Subjects in the Study

For Aim 3, we will recruit a total of 50 people to be randomized between two groups of 25 subjects; the waitlist control group (n=25) and the intervention group (n=25).

For the Annie pilot, a subset of the recruited patients will participate in developing and evaluating Annie texting to capture step counts, pain and mood.

[figure not shown]
10. Justification for the Use of Vulnerable Populations

Not applicable.

11. Study Design

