
 ▪ Perceptions about the strength and motivation for personalized goal-setting ▪ Perceptions about how well goal-setting is accepted by Veterans ▪ Perceptions of how goal-setting affects current practices or can be integrated into routine work flows ▪ Perceptions of how patient activation can be applied to improve outcomes ▪ Perceptions of how motivations to change and identifying meaningful goals can be aligned 	
 ▪ Availability of resources to carry out personalized goal-setting ▪ How training and fidelity assessment for personalized goal-setting fit with work demands ▪ Past experiences with collaborating with other VA health care providers (PACT and other) members on self-management or goal-setting ▪ Existing channels of communication for input and feedback among PACT members and other providers regarding goal-setting and self-management 	
 ▪ How to align roles in the project with existing responsibilities ▪ Perceptions about what successful implementation will require from staff, patients, and clinicians ▪ Perceptions of skills, attitudes, and beliefs about internal facilitators and study team ▪ Plans for establishing formal communication routines between study team, PACT members and other personnel

For the Annie texting pilot, we will use the VA Annie texting system. A select group of Veterans will be invited to participate in a technology program that involves texting participants to learn more about their health behaviors and status (specifically, step counts, pain and mood). There are two phases to this part of the study. The first phase (development) will involve asking up to five Veterans who completed MOTIVATE to give us feedback on usability and understandability of the proposed texting system. We will elicit opinions on a draft of a discussion guide that will outline the texts Veterans will receive from the Annie texting system. The second phase involves answering the texting questions to evaluate feasibility of the texting program (in a sample of 7-10 Veterans); this will be followed by in-depth semi-structured interviews to gather more information about barriers and facilitators of using the texting program.

12. Description of Procedures to be Performed

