In phase I (development) of the Annie texting-component of the study, we will ask for Veterans' and experts' feedback during telephone calls. Specifically, we will ask select Veterans who completed that MOTIVATE intervention about their experience with cell phone technology, experiences/difficulties of Annie (if used before), content of the proposed Annie texts, and suggestions for improvement regarding the content, frequency, and user-friendliness of the texts. Utilizing this feedback, a texting template and discussion guide for interviews will be finalized. In phase II, the intervention will be delivered via the Annie texting system to a select sample of Veterans in the waitlist control arm who have completed the end assessment, who have been offered the MOTIVATE sessions and who agree to participate in the Annie texting pilot. Veterans will receive a concise, phone-guided training on how to use the Annie texting system. Veterans will receive daily texts regarding step counts and three times weekly texts regarding pain/mood symptoms. Data, including both quantitative and qualitative, will be collected using Annie dashboard (will show response rates to specific text messages), surveys and semi-structured interviews, all conducted via telephone by a research team member. Afterwards, we will conduct semi-structured interviews over the telephone with up to 10 Veterans. Interviews will be audio-recorded (consent obtained upon enrollment in MOTIVATE). These audio-recordings will be securely transferred using a VA encrypted device (Apricorn Aegis Secure Key 3z 256 bit AES XTS Encryption 64 GB USB FIPS Level 3 Validated 140-2) to the UTSW Qualitative Research Committee who will transcribe and code the de-identified transcripts/ data. We will use NVIVO software for data management and coding of the transcripts. The same audio recorder, approved by IRB, from Aims 2 and 3 will be used.

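### The Section 8 inclusion list used to screen all trial candidates contains a smartphone item that only the Annie pilot needs, and the protocol does not say whether lacking one bars randomization

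*Combined protocol and SAP*

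**What the plan says.** **Eligibility.** Section 8 opens with "The eligibility criteria for all Veteran participants are as follows" and goes straight on to age, a back-pain code and the clinics. After a description of the recruitment routes comes one bulleted inclusion list, whose last item is "Has a smart phone with texting ability to participate in the Annie texting pilot". Annie has no eligibility list of its own. Section 12 refers back to the Section 8 criteria as those to be checked by telephone or in person.

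**What the main trial needs.** Section 5 says that "trained health coaches will deliver the intervention via telephone". Assessments are by telephone (Section 12), the binder and pedometer are mailed (Sections 12 and 11), and step counts are read out over the phone. The only other item about having a phone is the exclusion of people with no telephone.

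**Who takes part in Annie.** Section 9 says "we will recruit a total of 50 people to be randomized between two groups of 25 subjects", and that "a subset of the recruited patients will participate in developing and evaluating Annie texting". Section 5 puts Annie at 10-15 people. Phase 2 is to be run "in a sample of 7-10 Veterans". Section 12 draws them from "a select sample of Veterans in the waitlist control arm who have completed the end assessment", and Section 17 says that waitlist participants already in the trial will be contacted.

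**The outcome that could be touched.** Section 13 lists enrollment rates across primary care clinics first among the primary feasibility outcomes. Recruitment rates are to be estimated by the exact binomial method with 95% confidence intervals. No denominator is stated.

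**The concern.** A Veteran with a landline or basic phone could receive every coaching session and complete every assessment, yet would fail the inclusion list as it is written. If staff enforce the item, the trial would lose part of its stated population (Veterans aged 65 and over with chronic back pain and depression) for a reason unrelated to the intervention. Section 6 itself gives the exclusion of older adults from trials as part of the rationale. The enrollment figures meant for planning the next trial could then partly reflect device ownership. The recruitment flyer is to outline the eligibility criteria, so if it carries this item it could also deter some Veterans before any screening.

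If some staff enforce the item and others do not, the people screened will not have met one common standard.

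**Working it through.** The documents contain no enrollment target and no smartphone-ownership rate, so there is no stated figure to reproduce. Ownership among otherwise eligible Veterans, *s*, is an assumption throughout, with 60-90% as the working range.

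**1. Timing.** Under Section 12, screening and the baseline assessment come before randomization. Annie phase 2 is filled from the waitlist arm after the end assessment. At screening, therefore, nobody can be identified as a future phase 2 participant. A screener can only apply the item to everyone or set it aside for everyone, and the protocol does not say which.

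**2. Share of the trial that Annie involves.**
- All of Annie: 10/50 = 20% to 15/50 = 30%.
- Phase 2 only: 7/50 = 14% to 10/50 = 20% of the trial, or 7/25 = 28% to 10/25 = 40% of the waitlist arm.

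**3. Recruitment burden if the item is enforced on all.** Otherwise eligible Veterans needed to enrol 50 = 50/*s*.
- *s* = 0.90: 50/0.90 = 55.6, so 56 (10% turned away).
- *s* = 0.60: 50/0.60 = 83.3, so 84 (40% turned away).

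**4. Effect on the enrollment rate.** This depends on the denominator.
- *Veterans approached, item enforced:* the rate is multiplied by *s*, assuming that ownership is unrelated to willingness. The table uses an assumed 20% rate without the item, and exact 95% intervals.

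| Assumed *s* | Enrolled / approached | Rate (95% CI) |
|---|---|---|
| item not applied | 50/250 | 20.0% (15.2-25.5) |
| 0.9 | 50/278 | 18.0% (13.7-23.0) |
| 0.7 | 50/357 | 14.0% (10.6-18.0) |
| 0.6 | 50/417 | 12.0% (9.0-15.5) |

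- *Eligible Veterans only, item enforced:* no change unless ownership is related to willingness.
- *Item applied to Annie only:* no effect.

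**5. Would an Annie-only criterion leave enough owners?** Expected owners in the waitlist arm = 25*s*: 25 × 0.6 = 15 and 25 × 0.9 = 22.5. With the number of owners taken as binomial (25, *s*), and two values below the working range added as a stress test:

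| Assumed *s* | P(at least 7 owners) | P(at least 10 owners) |
|---|---|---|
| 0.4 | 0.926 | 0.575 |
| 0.5 | 0.993 | 0.885 |
| 0.6 | about 1.0 | 0.987 |
| 0.7 | about 1.0 | 0.9995 |

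These count owners only. With 15 owners, filling phase 2 requires 7/15 = 47% to 10/15 = 67% of them to remain in the study and agree.

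**The case against.** The strongest reply is that the item applies to Annie only and says so. It carries its own purpose clause. The exclusion for having no telephone would be nearly redundant if every participant needed a smartphone. Section 17 recruits for Annie from people already in the trial, which is close to what a separate criterion would require. The Section 8 sentence about all Veteran participants is followed by its own content and does not directly introduce the bullets. All of this stands, and it makes an Annie-only intent plausible. A reader might infer from the list that all 50 participants must own smartphones; the documents do not establish that.

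The reply also limits the consequences. A reader might infer that the enrollment rate is distorted, but Section 13 fixes no denominator, and under two of the three cases in the check there is little or no effect. A reader might go further and say that adherence and retention would not carry over to the next trial. Nothing in the documents supports that: delivery is by telephone, and no reason is given why smartphone owners should adhere differently.

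The reply does not supply a statement that a Veteran with a telephone and no smartphone may be randomized. The list is the operative screen, Annie membership is unknown when it is used, and the two readings give opposite decisions for the same person.

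**Conclusion.** The point holds as a misplaced criterion of uncertain scope. Read literally, the list excludes Veterans who could receive the whole intervention, which could limit generalizability to Veterans aged 65 and over and could lower an enrollment rate counted over Veterans approached. At an assumed 60-90% ownership, about 56-84 otherwise eligible Veterans would be needed to enrol 50. That size rests on an ownership range the documents do not give and on the item being enforced at trial screening; if it is applied to Annie only, the effect is nil.

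It would be wrong to infer bias in the comparison of the two arms. The item would act before randomization and on both arms alike.

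**What to change.** Take the item out of the Section 8 trial inclusion list and place it under a separate heading for Annie phase 2 only, applied when waitlist participants are invited. Record smartphone ownership at baseline for everyone. If anyone has already been screened out under the item, report that number with the enrollment rate and say whether the rate's denominator is Veterans approached or Veterans eligible.

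The cost is a one-line amendment and one baseline field. The real trade-off is a smaller pool for Annie phase 2: smartphone owners in the waitlist arm, about 15 of 25 at 60% ownership, before attrition and refusal. That is usually still enough for 7-10, though the margin for 10 becomes thin if ownership falls well below the assumed range.
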